8.3 Analysis of Safety Data

The Safety population will be used for the analysis of safety assessments.

8.3.1 Adverse Events

Adverse events will be coded using the most recent version of Medical Dictionary for Regulatory Activities (MedDRA). Treatment Emergent AE's (TEAE) are defined as events with an onset on or after the first treatment. TEAEs will be summarized by System Organ Class and preferred term by treatment group. The following TEAE summaries will be provided:

- Overall (i.e., regardless of severity or relationship to treatment);
- By intensity (mild, moderate, severe, life threatening or death);
- By causality (definitely, probably, possibly, unlikely or unrelated);

• By impact on study treatment (dose increased, dose not changed, dose rate reduced, dose reduced, drug interrupted, drug withdrawn, not applicable, or unknown).

In addition, separate summaries of serious adverse events, and adverse events resulting in discontinuation of study treatment will be presented.

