1.4.2.2. PRO 140 1102 Study

For PRO 140 1102, the majority of AEs, other than injection-site reactions, were considered mild and possibly related to drug administration. The majority of injection-site reactions were considered mild, self-resolving, and definitely related to drug administration. PRO 140 derived from Chinese Hamster Ovary (CHO) cells and administered at 100 mg/mL was generally well tolerated in healthy, normal volunteers. Overall, PRO 140 administered SC using Autoject® 2 appeared better tolerated than manual injection.

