6.1.3. Leronlimab (PRO 140) - Administration

Guidelines for dose preparation can be found in the pharmacy manual.

Leronlimab (PRO 140) or placebo will be provided to the administering personnel in single-use syringes prepared from vials of study drug stored at 2-8°C at the site pharmacy prior to use. Syringes will be prepared by an unblinded pharmacist or designated site staff. Each of two syringes is filled to deliver 2 mL of study drug.

Equivalent volumes of PRO 140 will be administered subcutaneously on opposite sides of the abdomen.

A 20-guage needle should be used to remove PRO 140 from vial and a 25-guage needle is used for administration to subjects.

Note: After the leronlimab solution is drawn into the syringe, it can be stored at room temperature (20°C to 25°C, 68°F to 77°F) for up to 2 hours, or refrigerated (2°C to 8°C, 36°F to 46°F) for up to 4 hours.

IP should be administered slowly over 15 seconds per mL.

Following each SC delivery of drug, careful examination will be made to assess the appearance of any study drug Injection Site Reactions (ISRs) as per CTCAE v5.0.

Leronlimab (PRO 140) will be administered as SC injection by a qualified medical professional at the study clinic.

Note: It is preferred that the same injection site be used throughout the study. At the same time, it is not recommended to inject the study drug into areas where skin shows signs of a previous injection site reaction. It is advised to change the injection site if any previous injection site reaction remains unresolved.

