6.1.4. Leronlimab (PRO 140) - Post Injection Monitoring

Subject will be observed at approximately 30 minutes post-injection or longer if necessary, for injection site reaction as per CTCAE v5.0.

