9.1. ADVERSE EVENT (AE)

An adverse event (AE) is defined as any unfavorable or unintended sign, symptom, or disease that occurs or is reported by the patient to have occurred, or a worsening of a pre-existing condition. An adverse event may or may not be related to the study treatment.

AEs will be elicited through direct questioning and subject reports. Any abnormality in physical examination findings or laboratory results that the investigator believes is clinically significant (CS) to the research subject and that occurred after initiation of the first study treatment will be reported as AEs. Abnormal findings that are NOT clinically significant should not be recorded as an AE.

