8.3.5 Physical Examination

All abnormal physical examination finds will be listed.

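### Protocol 9.1 leaves it unclear whether an examination-only Grade 1 injection-site reaction is recorded, and the SAP plans no injection-site summary by arm, so mild reactions may be under-counted to an unknown extent

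*Combined protocol and SAP*

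**What the plan says.** **Assessment.** Protocol 6.1.3 requires that after each subcutaneous delivery "careful examination will be made to assess the appearance of any study drug Injection Site Reactions (ISRs) as per CTCAE v5.0". Protocol 6.1.4 adds: "Subject will be observed at approximately 30 minutes post-injection or longer if necessary, for injection site reaction as per CTCAE v5.0". Table 6-3 gives injection-site reactions (ISRs) their own management table by grade, separate from all other toxicities.

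**Recording.** Protocol 9.1 opens with a broad definition of an adverse event (AE): "any unfavorable or unintended sign, symptom, or disease that occurs or is reported by the patient to have occurred", or a worsening of an existing condition. It then says that examination or laboratory abnormalities are reported as AEs when the investigator considers them clinically significant, and ends: "Abnormal findings that are NOT clinically significant should not be recorded as an AE". Table 9-1 includes Grade 1, which covers asymptomatic or mild events that need no intervention.

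**Analysis.** SAP 8.3.1 states: "TEAEs will be summarized by System Organ Class and preferred term by treatment group". It adds summaries by intensity (mild included), causality and impact on treatment. SAP 8.3.5 says of physical examination only: "All abnormal physical examination finds will be listed". The table list in SAP 9.2 names no ISR table; its last entry is an undefined heading for other safety data. SAP 8 puts all collected data in by-subject listings.

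**The concern.** The protocol requires a graded assessment after every dose, but its recording rule and its analysis plan do not carry that assessment through. An investigator who sees faint redness at the 30-minute check can grade it 1, judge it not clinically significant, and follow the last sentence of 9.1 by not recording an AE. Another investigator can rely on the opening definition and Table 9-1 and record it. Both have followed the protocol.

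At stake is the local-tolerability comparison of 700 mg weekly with placebo. Safety is part of the stated objective. The placebo is saline and the active product is an antibody in a histidine, glycine and polysorbate buffer (Protocol 6.1), so a difference in local reactions is plausible. In the earlier 1102 study, "The majority of injection-site reactions were considered mild, self-resolving, and definitely related to drug administration". For the CD03 study, Protocol 1.4.2.11 compares ISR frequency and severity across dose groups, but that study had no placebo arm. Laboratory values, vital signs and ECG all have defined grade, shift or threshold summaries in SAP 8.3.2 to 8.3.4; ISRs have none.

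A secondary reason is that subjects rate the primary endpoint themselves. The ISR difference between arms would help in judging whether local reactions could have hinted at allocation.

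**Working it through.** The documents give no ISR rate, target or precision for this trial, so there is no stated figure to reproduce. The check is a comparison of sections, plus a count of the assessments involved.

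**1. Volume of planned checks.** Inputs: 50 subjects randomized 1:1 (Protocol 8.3), 8 weekly doses (Table 6-1), two injections per dose (Table 6-2).

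- Subjects per arm: 50 / 2 = 25.
- Dose visits: 25 x 8 = 200 per arm; 50 x 8 = 400 in total.
- Injections: 200 x 2 = 400 per arm; 400 x 2 = 800 in total.

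The note under Table 6-2 lets a dose be given as four injections in some subjects, so dose visits are a steadier denominator than injections.

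**2. Route of each kind of reaction.**

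| Reaction | Recorded as an AE? | Summarized by arm? |
|---|---|---|
| Reported by the subject (e.g. pain, itching), any grade | Yes, under the opening definition in 9.1 | Yes, SAP 8.3.1 |
| Seen on examination, judged clinically significant | Yes, 9.1 | Yes, SAP 8.3.1 |
| Seen on examination only, Grade 1, judged not clinically significant | Unclear: the opening definition and Table 9-1 point to yes, the last sentence of 9.1 to no | Only if recorded as an AE |

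**3. Fallback for the third row.** The schedule of assessments (Table 4-2) has no ISR row, and no section says where a grade is entered if the reaction is not an AE. At best such a reaction would reach a by-subject listing. The CRF is not among the documents and may contain a field that the protocol does not mention. Table 4-2 also marks adverse events only from V3, although Protocol 4.2.1 calls for AE review after the first dose at V2.

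**4. What the TEAE tables can show.** The SAP does not say how ISRs will be coded. If they fall under more than one preferred term, a subject can appear in several rows, and the rows cannot be added to give subjects with any ISR. No specified row gives maximum ISR grade per subject.

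**5. Effect on the comparison.** Let p_A and p_P be the true proportions of subjects with any ISR, and s_A and s_P the shares of those subjects with at least one ISR recorded as an AE. The expected visible difference is s_A p_A - s_P p_P. If both shares equal s, this is s(p_A - p_P): the difference shrinks by the factor s and the ratio is unchanged. If the shares differ, both are distorted. The documents give none of these four quantities.

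**The case against.** The strongest reply is that the protocol already treats ISRs as AEs. The opening definition in 9.1 carries no clinical-significance test. The filter is introduced for physical examination and laboratory findings, whereas the site checks sit under drug administration and post-injection monitoring. Table 6-3 itself calls a Grade 2 ISR an AE, and the account of the 1102 study counts ISRs among AEs. Any ISR so recorded appears by arm in the preferred-term and intensity tables. In a 50-subject exploratory trial, a dedicated table may seem optional.

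Most of this stands, and it confines the gap to Grade 1 reactions found only on examination. It does not close that gap: the last sentence of 9.1 speaks of abnormal findings without exempting site checks. Nor does it supply a count of subjects with any ISR.

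A reader might infer more than the documents support:

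- **That ISRs are the drug's main known harm.** The definite attribution comes from one early study. Protocol 1.6 lists ISRs after allergic and flu-like reactions, 1.3 reports no pattern of drug-related toxicity, and 1.4.2.11 describes ISRs as comparable at 350, 525 and 700 mg.
- **That most ISRs would go unreported.** That needs a recorded share below 50%, and no figure for that share is given. The mild share in CD01 (70/87, printed as 80.4%) covers all recorded AEs, not ISRs, and shows that mild events were recorded there.
- **That the number of missed subjects can be projected.** Both the ISR rate and the recorded share would have to be assumed.

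The link to guessing of allocation is also conjecture.

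**Conclusion.** The point holds in a limited form. Protocol 9.1 does not settle whether an examination-only Grade 1 ISR judged not clinically significant is recorded, and this conflicts with the grading required by 6.1.3 and 6.1.4 and with Table 9-1. The SAP specifies no row for subjects with any ISR or for maximum ISR grade. Such reactions may be under-counted by arm, to an extent that the documents do not let one estimate; it could be negligible if sites record every graded reaction. The 200 planned dose visits per arm measure how many checks are affected, not how many reactions would be lost. The conclusion assumes that no CRF field or completion guideline outside these documents already captures every graded reaction. This is a worthwhile, inexpensive improvement to the safety reporting, and it does not undermine the trial's safety analysis as a whole.

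**What to change.** **Protocol 9.1.** Reconcile the last sentence with 6.1.3, 6.1.4 and Table 9-1 by stating that every ISR of CTCAE Grade 1 or higher is recorded whatever its clinical significance, and say where (AE form or a site-check field).

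**SAP 8.3.1 and 9.2.** Add one table by arm in the Safety population, covering every graded ISR:

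- subjects with at least one ISR of any type;
- those subjects by maximum CTCAE grade;
- dose visits with an ISR divided by doses given.

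**Cost.** The examinations are already required. The report will show more Grade 1 events, so local tolerability may look slightly less favourable, and one CRF field may be needed. No dose or management rule changes. The table can be specified at any time before unblinding. The recording clause works only from its adoption, and earlier checks can be recovered only where source documents hold the grade.

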8.3.2 Clinical Laboratory Evaluations

All available results of the clinical laboratory evaluations will be listed and/or summarized. Laboratory evaluations include hematology, biochemistry, serology and urinalysis.

Laboratory data will be classified into grades according to DAIDS toxicity grading. A severity grade of 0 will be assigned when the value is within normal limits.

The following summaries will be produced for the hematology and biochemistry laboratory data (by laboratory parameter):

- Number and percentage of patients with worst post-baseline grade (regardless of the baseline status). Each patient will be counted only for the worst grade observed post-baseline
- Shift tables using DAIDS grades to compare baseline to the worst post-baseline value will be produced for hematology and biochemistry laboratory parameters with DAIDS grades
- Shift tables using normal range to compare baseline to the worst post-baseline value will be produced for hematology and biochemistry laboratory parameters without DAIDS grades

8.3.3 Vital Signs

Vital sign assessments are performed in order to characterize basic body function. The parameters collected in this study are: systolic BP (mmHg), diastolic BP (mmHg), temperature (0 C), heart rate (bpm), respiratory rate (rpm), pulse oxygen.

8.3.3.1 Clinically notable elevated values

- Systolic BP: ≥ 160 mmHg and an increase ≥ 20 mmHg from baseline
- Diastolic BP: \geq 100 mmHg and an increase \geq 15 mmHg from baseline.
- Body temperature: ≥ 39.1°C
- Heart rate: ≥ 120 bpm with increase from baseline of ≥ 15 bpm
- Respiration rate: \geq 24 breaths per minute with increase from baseline of \geq 6 breaths per minute

8.3.3.2 Clinically notable below normal values

- Systolic BP: \leq 90 mmHg and a decrease \geq 20 mmHg from baseline
- Diastolic BP: ≤ 50 mmHg and a decrease ≥ 15 mmHg from baseline

- Body temperature: ≤ 35°C
- Heart rate: ≤ 50 bpm with decrease from baseline of \geq 15 bpm
- Respiration rate: < 8 breaths per minute with decrease from baseline of ≥ 6 breaths per minute
- Oxygen Saturation: < 94%

Number and percentage of patients with at least one post-baseline vital sign abnormality (in both directions, i.e. both elevated and below normal values) will be summarized for heart rate, diastolic BP and systolic BP by treatment group.

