3.3.2. Exclusion Criteria

Potential subjects meeting any of the following criteria will be excluded from enrollment:

- 1. Exhibiting signs of moderate or severe pulmonary disease (such as COPD, asthma, or pulmonary fibrosis)
- 2. Ongoing requirement of oxygen therapy
- 3. Pulse oxygen saturation (SpO2) of <94% on room air at the time of screening
- 4. History of splenectomy
- 5. Liver cirrhosis or patient showing signs of clinical jaundice at the time of screening
- 6. Chronic kidney disease stage 4 or requiring dialysis at the time of screening

CONFIDENTIAL Page 42 of 101

- 7. NYHA Class III or IV congestive heart failure (CHF)
- 8. Exhibiting signs of uncontrolled hypo-or hyper- thyroidism at the time of Screening
- 9. Uncontrolled rheumatologic disorders at the time of screening
- 10. History of organ transplantation or are candidates for organ transplantation at the time of screening
- 11. History of Chronic Fatigue Syndrome prior to COVID19 infection
- 12. History of fibromyalgia prior to COVID-19 infection
- 13. History of major psychiatric disorder including bipolar disorders, schizophrenia, schizoaffective disorder, major depression. Patients with major depression can be enrolled if patient has had no episode within the past year or is considered in remission or controlled by treatment.
- 14. Any malignancy within the past 5 years, excluding successfully treated basal cell carcinoma or squamous cell carcinoma without evidence of metastases.
- 15. Any other clinically significant serious systemic diseases which would interfere with study conduct or study results interpretation per the Investigator.
- 16. Treatment with immunosuppressive or immunomodulatory medications within 5 half-lives prior to screening. Patients on replacement therapy for adrenal insufficiency will be allowed. Patients on stable (> 3 months) low dose corticosteroid ≤ 5 mg Prednisone will be allowed.
- 17. History of allergic reactions attributed to compounds of similar chemical or biologic composition to leronlimab (PRO 140) are not eligible
- 18. Ongoing use of CCR5 antagonist
- 19. Inability to provide informed consent or to comply with test requirements
- 20. Consideration by the investigator, for safety reasons, that the subject is an unsuitable candidate to receive study treatment
- 21. Pregnancy or breast feeding
- 22. Participating in another study for an investigational treatment

CONFIDENTIAL Page 43 of 101

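### The SAP sets notable-value limits for six vital signs but plans a by-arm count for only three, so the limits for temperature, respiration rate and SpO2 feed no planned count.

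*Combined protocol and SAP*

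**What the plan says.** SAP 8.3.3 lists the vital signs collected: systolic and diastolic pressure, then "temperature (0 C), heart rate (bpm), respiratory rate (rpm), pulse oxygen". SAP 8.3.3.1 gives high limits for five of them, including "Body temperature: ≥ 39.1°C" and a respiration rate of at least "24 breaths per minute with increase from baseline of" 6 or more. SAP 8.3.3.2 gives low limits for all six, including "Body temperature: ≤ 35°C", "Respiration rate: < 8 breaths per minute with decrease from baseline of ≥ 6 breaths per minute" and "Oxygen Saturation: < 94" per cent.

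The same section closes by planning the number and percentage of subjects with at least one post-baseline abnormality in either direction. It confines that table to three signs: the counts "will be summarized for heart rate, diastolic BP and systolic BP by treatment group".

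Protocol 8.10.6.4 requires only that vital signs be listed and/or summarized by arm. SAP 9.2 carries a vital signs table heading with no detail. Protocol 3.3.2 item 3 excludes "Pulse oxygen saturation (SpO2) of <94% on room air at the time of screening".

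**The concern.** A limit that feeds no table does no work. Five of the 11 limits are in that position, and the SAP gives no reason for stopping at heart rate and blood pressure.

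The neighbouring safety sections do not stop short in this way. SAP 8.3.4 counts subjects with notable values for every ECG parameter that has a limit. SAP 8.3.2 tabulates the worst post-baseline grade for hematology and biochemistry.

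The omitted signs matter to this trial's safety picture. SAP 3.4 names temperature and respiratory rate among the safety measures. Protocol 1.6 lists fever among the flu-like reactions sometimes seen with monoclonal antibodies. Protocol 12 states that the data safety monitoring committee section does not apply, and Protocol 8.8 plans no interim analysis, so the final by-arm tables carry the aggregate safety comparison. What would be missing is a simple statement, by arm, of how many subjects crossed each of these limits.

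**Working it through.** The plan states no figure to reproduce here, since the sample size rests on clinical judgment without a power calculation. The check is a comparison of two lists, plus a count of readings.

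**Limits defined against limits counted** (SAP 8.3.3.1 and 8.3.3.2)

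| Vital sign | High limit | Low limit | Change-from-baseline condition | In the by-arm count |
|---|---|---|---|---|
| Systolic BP | yes | yes | yes | yes |
| Diastolic BP | yes | yes | yes | yes |
| Heart rate | yes | yes | yes | yes |
| Respiration rate | yes | yes | yes | no |
| Temperature | yes | yes | no | no |
| SpO2 | none | yes | no | no |

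- Limits defined: 5 high + 6 low = 11.
- Limits counted: 3 signs × 2 directions = 6.
- Limits not counted: 11 − 6 = 5, belonging to 6 − 3 = 3 signs.

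**Readings of SpO2 after the first dose** (Protocol 7.10; Table 4-2, footnote 5)

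- V2 post-dose: 1.
- V4, V6, V8, V10, V12, V14, V16: 7.
- V17 and V18: 2.
- Total 1 + 7 + 2 = 10 time points. With all 50 subjects dosed and no dropout, 10 × 50 = 500 readings at most. The V2 post-dose reading belongs here because SAP 7.1 sets baseline as the last value before treatment.

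**Whether another planned output supplies the count**

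- By-subject listings (SAP 8) give the values but no count by arm.
- Continuous summaries (SAP 8.1) show minimum and maximum, so an extreme may be visible, but not how many subjects reached it.
- The exploratory SpO2 analysis (SAP 3.3 and 8.2.3) compares change from baseline at Days 7 to 56. It leaves out the V2 post-dose and V18 readings and counts no threshold crossings.
- Adverse event tables (SAP 8.3.1) are by arm, but Protocol 9.1 keeps abnormal findings judged not clinically significant out of the adverse event record. They do not apply the SAP's limits.

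**Illustration of the mean-change point** (assumed figures). Take 25 subjects per arm, with k of them falling 4 SpO2 points and the rest unchanged. Mean shift = −4k/25.

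- k = 1: −0.16 points.
- k = 3: −0.48 points.
- k = 5: −0.80 points.

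A shift of half a point or less would not reveal that 3 of 25 subjects (12%) had each fallen 4 points.

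**Would a count have anything to show?** If the true rate of crossing a limit is p, the chance of at least one case among 25 is 1 − (1 − p)^25. The documents give no rate, so p is assumed over a range.

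- p = 2%: 40%.
- p = 5%: 72%.
- p = 10%: 93%.
- p = 20%: over 99%.

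**The case against.** The strongest reply is that nothing here contradicts the protocol, which allows vital signs to be listed and/or summarized, and that with 50 subjects the listings can be read by eye. No efficacy endpoint, sample size or stopping rule depends on this table. All of that stands, and it keeps the point small. It does not supply the missing count.

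Three stronger readings are tempting, and the documents do not support them.

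- A reader might infer that no comparison between arms of desaturation, fever or fast breathing would appear at all. That goes too far: recorded adverse events are tabulated by arm, SpO2 change is summarized by arm at eight time points, and continuous summaries may show the extremes.
- A reader might infer that every later SpO2 below 94% is a new event, because such subjects are excluded. The exclusion is tied to screening. Baseline is normally the V2 pre-dose value, up to seven days later. Footnote 6 of Table 4-2 applies the symptom-score criterion at both V1 and V2, but the SpO2 exclusion does not name V2. A baseline below 94% is therefore possible, and a move from 94% to 93% would also meet the limit.
- A reader might infer that the omitted signs are the most relevant ones because this is a respiratory population. Inclusion criterion 3 spans five symptom groups, so a subject can enter with no respiratory symptom, and moderate or severe pulmonary disease is excluded. A feeling of fast heartbeat is itself a listed symptom, so heart rate, which is counted, is relevant too.

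**Conclusion.** The gap is real and narrow. Three of six vital signs, and five of 11 limits, have no planned by-arm count of subjects crossing them, and no other planned output provides one. This rests on reading the closing sentence of SAP 8.3.3.2 as it is written, as a restriction to the three signs it names; the undetailed vital signs heading in SAP 9.2 does not widen it. The figure of 500 SpO2 readings is a maximum that assumes full dosing and no dropout. The mean-shift and detection figures are illustrations under assumed inputs, not estimates for this trial. The consequence is a less complete safety comparison. No efficacy conclusion changes, so this is a worthwhile improvement rather than a defect that threatens the trial.

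**What to change.** Before unblinding, amend the closing sentence of SAP 8.3.3.2 so that the by-arm number and percentage covers all six signs: systolic BP, diastolic BP, heart rate, temperature, respiration rate and SpO2.

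For SpO2 and temperature, add a split by whether the subject's baseline value already met the limit, so that new events can be told from persisting ones. Respiration rate needs no such split, because its limits already require a change from baseline.

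The limits, visits and data collection do not change. The cost is a few more rows in a table already planned, and making the change before unblinding keeps the added counts prespecified.
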